#### **5.5.3.2 Handling of other study treatment**

Not applicable.

#### **5.5.4 Instructions for prescribing and taking study treatment**

Study treatment (150 mg secukinumab) will be administered s.c. by 1 mL PFS throughout the study as 150 mg / 1 mL secukinumab.

Administration of study treatment will be allowed to occur via self-injection at the study site through Week 48. Administration of study treatment must occur after the study assessments for the visits that have been completed. The PFS with the ready-to-use study treatment solution will be provided by the site staff to the patient. Detailed instructions on the self-administration of the study treatment will be described in the IFU for secukinumab and provided to each patient.

If the patient is not comfortable self-injecting the study treatment, then the site can administer it for the patient.

At the BSL visit, patients will be instructed by the site staff, utilizing the IFU, on how to self-inject using a PFS. Patients will be asked to raise any questions and then to proceed with self-injection.

At the Week 1 visit, patients will be asked to refer to the IFU and to proceed directly with self-injection of the study drug (i.e., no prior retraining) for the remainder of the trial. However, if the patient is not comfortable self-injecting the study treatment, then the site staff may administer it for the patient. Any event related to self-injection should be reported appropriately.

Administration of investigational treatment should occur after sample collection for PK assessments at visits specified in [Table 6-1](#).

The investigator should promote compliance by instructing the patient to attend the study visits as scheduled and by stating that compliance is necessary for the patient's safety and the validity of the study. The patient should be instructed to contact the investigator if he/she is unable for any reason to attend a study visit as scheduled.

### **5.5.5 Permitted dose adjustments and interruptions of study treatment**

Study treatment dose adjustments are not permitted. Study treatment interruption is although not permitted with the following exceptions: Study treatment interruption is only permitted if, in the opinion of the investigator, a patient is deemed to be at a significant safety risk unless administration of investigational treatment is temporarily interrupted. In such cases study treatment should be interrupted only during the time that this risk is present and ongoing. Study treatment can be restarted at the next scheduled visit after resolution of the safety risk. The effect of secukinumab on live vaccines is unknown; therefore live vaccines should not be administered during participation in the study. In case a live vaccine has been administered due to a medical urgency, study treatment should be interrupted for 12 weeks. Any study treatment interruption must be recorded on the corresponding eCRF page.

### **5.5.6 Rescue medication**

Rescue medication is defined as any new therapeutic intervention or a significant change to ongoing therapy made because a patient is experiencing either no benefit from participation in the trial or worsening/exacerbation of their disease. Rescue medication must not be used before completion of Week 16 assessments. Although no patient will be restricted from receiving necessary rescue medications for lack of benefit or worsening of disease, if rescue with prohibited biologics (as described in [Section 5.5.8](#)) occurs, patients will be discontinued from the study. Efficacy will be assessed in detail at every study visit, and patients who are deemed not to be benefiting from the study treatment based on safety and efficacy assessments (see [Section 5.5.9](#)) or for any reason on their own accord will be free to discontinue participation in the study at any time. Changes in NSAID concomitant therapy are permitted as per investigator's clinical judgment after all Week 16 assessments are completed. Please see [Section 5.5.7](#), [Section 5.5.8](#) and [Section 5.5.9](#) for further details.

Any use of rescue medication must be recorded in the Prior/Concomitant medications eCRF page.

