#### **Methotrexate**

Patients taking MTX ( $\leq 25$  mg/week) must be on a stable dose for at least 4 weeks before baseline and maintained stable until Week 52.

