### **5.5.8 Prohibited Treatment**

Use of the treatments displayed in [Table 5-1](#) is NOT allowed after the start of the washout period unless otherwise specified below.

Live vaccines should not be given until 12 weeks after last study treatment administration.

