**Table 5-1      Prohibited treatment**

Prohibited treatments	Washout period (before BSL)
Etanercept*	4 weeks
Infliximab*	8 weeks
Adalimumab, golimumab, certolizumab*	10 weeks
Unstable dose of MTX or sulfasalazine (until Week 52)	4 weeks
Other DMARD (except MTX or sulfasalazine)	4 weeks
Leflunomide	8 weeks
Leflunomide with Cholestyramine washout	4 weeks
Unstable dose of NSAIDs (COX1 or COX2 inhibitors) (until Week 16)	2 weeks
Systemic corticosteroids > 10 mg prednisone equivalent** (until Week 16)	2 weeks
Intra-articular steroid injections (until Week 16)	4 weeks
Any investigational treatment or participation in any interventional trial	4 weeks or 5 half-lives (whichever is longer)
Analgesics other than paracetamol/acetaminophen or low strength opioids PRN	4 weeks
Live vaccinations	6 weeks

\* These agents fall under the category of biologic immunomodulators and are prohibited medications. Administration of these agents requires study discontinuation (see [Section 5.5.9](#)).

\*\* See details about corticosteroid management in [Section 5.5.7](#).

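### After Week 16 the protocol gives three unreconciled instructions on a DMARD start or change for worsening, and the SAP has no rule for a rescued patient who stays in

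*Protocol*

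**What the plan says.** **Protocol 5.5.6 (rescue).** Rescue is "any new therapeutic intervention or a significant change to ongoing therapy made because a patient is experiencing either no benefit" from the trial, or is getting worse. On timing: "Rescue medication must not be used before completion of Week 16 assessments". On breadth: "Although no patient will be restricted from receiving necessary rescue medications for lack of benefit or worsening of disease". The same sentence goes on to the one stated consequence, "if rescue with prohibited biologics (as described in" section 5.5.8), which is discontinuation from the study. The section expressly permits NSAID changes after Week 16 and refers to 5.5.7, 5.5.8 and 5.5.9 for further detail.

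**Protocol 5.5.7 (concomitant treatment).** Patients taking methotrexate (MTX) "must be on a stable dose for at least 4 weeks before baseline and maintained stable until Week 52". The sulfasalazine paragraph has the same rule.

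**Protocol 5.5.8 and Table 5-1 (prohibited treatment).** Use of a listed treatment "is NOT allowed after the start of the washout period unless otherwise specified below". The list includes "Unstable dose of MTX or sulfasalazine (until Week 52") and "Other DMARD (except MTX or sulfasalazine"), with leflunomide in its own rows. The last two carry no end week. The footnote requiring study discontinuation applies only to the asterisked biologics.

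**Protocol 5.5.9 (discontinuation of study treatment).** After its list of mandatory reasons, it says the investigator should stop study treatment in a patient who is not improving or is worsening.

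**SAP 2.5.3 and 2.7.3.** For binary efficacy variables up to Week 52, non-response is assigned in two cases: the patient has dropped out, or the data needed to compute response are missing. Rescue is not mentioned.

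**The concern.** Take a patient who worsens after Week 16 and for whom the investigator wants to start a DMARD or raise the dose of one. Section 5.5.6 describes this as rescue that will not be restricted. Table 5-1 describes it as not allowed, and 5.5.7 adds a stability rule for MTX and sulfasalazine. Section 5.5.9 says to stop study treatment. An investigator cannot follow all three.

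The statistical consequence falls on results after Week 16. The study's stated purpose covers efficacy up to 52 weeks, SAP 2.1 plans efficacy by week up to Week 52, and SAP 2.14 plans a Week 52 interim analysis to support filing. If the patient receives the DMARD and stays, later response is scored on observed values and may partly reflect the added drug. If the patient leaves, the same patient is a non-responder. The tables would not show which had happened.

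**Working it through.** **1. The plan's own figure.** The only design figure is the lower 95% limit for ASAS 20 at Week 16 (Protocol 9.7; SAP section 3), with n = 30 and an assumed rate of 60%:

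0.60 − 1.96 × √(0.60 × 0.40 / 30) = 0.425, or 42.5%.

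It reproduces. It concerns Week 16 only, and rescue is barred until the Week 16 assessments are complete, so this point does not touch it.

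**2. The sections side by side, for an act taken because of worsening after Week 16.**

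| Act | 5.5.6 | 5.5.7 | Table 5-1 | 5.5.9 |
|---|---|---|---|---|
| Dose change of MTX or sulfasalazine in a patient already taking it | Meets the rescue definition if significant; not restricted | Dose to be stable to Week 52 | Not allowed to Week 52 | Stop study treatment |
| New start of MTX or sulfasalazine | Meets the rescue definition; not restricted | Silent | Caught only if a new start is read as an unstable dose | Stop study treatment |
| Start of another DMARD or leflunomide | Meets the rescue definition; not restricted | Gives leflunomide washout only | Not allowed; no end week | Stop study treatment |

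The first and third rows contradict directly. The second is ambiguous.

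**3. Does any text break the tie?**
- The only exception in 5.5.8 is for what is specified below it. Section 5.5.6 stands above it, and nothing below exempts rescue.
- The cross-reference at the end of 5.5.6 does not say that the later sections limit rescue.
- The NSAID row, the row for systemic corticosteroids above 10 mg and the intra-articular steroid row all end at Week 16. The DMARD rows do not.
- No consequence is stated for a non-biologic breach. Study discontinuation is attached to biologics in 5.5.6 and the Table 5-1 footnote, and 5.5.9 lists biologic use among its mandatory reasons for stopping study treatment.

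**4. What the SAP does with the patient.** The heading of SAP 2.4 names rescue medication, but no rescue analysis follows. SAP 2.4.2 tabulates ankylosing spondylitis therapy by category without a DMARD category, and counts drugs continued from before baseline together with drugs started later. A DMARD started or changed as rescue is therefore not visible, and is not linked to response.

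**5. Size per patient.** In the non-responder analysis the denominator is the full analysis set, so one patient is 1/30 = 3.3 points.

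Illustration under the plan's 60%: 30 × 0.60 = 18 responders and 12 non-responders at Week 16. Suppose the 18 keep their response and k of the 12 are given a DMARD, stay and meet the criterion later. The later rate is (18 + k)/30, against 18/30 = 60% if those k are non-responders.

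| k (assumed) | Rate |
|---|---|
| 0 | 60.0% |
| 1 | 63.3% |
| 3 | 70.0% |
| 6 | 80.0% |
| 12 | 100.0% |

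The documents give no value for k. In the observed-case analysis (SAP 2.5.4) a patient who has left also leaves the denominator, so the 3.3 points applies to the main analysis only.

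**The case against.** The strongest reply is that the sections can be read as one scheme. Section 5.5.6 sends the reader to 5.5.7 to 5.5.9; the one change it expressly permits after Week 16 is to NSAIDs; and the staggered end weeks in Table 5-1 look like a deliberate list of what may change and when. On that reading the sentence on not restricting rescue only assures that necessary care is not withheld. The worsening patient stops study treatment under 5.5.9, receives a non-biologic outside the study as 5.5.13 allows, and is a non-responder from drop-out. This reading is possible, but no text states it, and it gives the no-restriction sentence little effect inside the study. It is a reason to write the rule down.

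Other parts of the reply stand, and they limit the point:
- A reader might infer that 5.5.7 forbids starting or changing any DMARD through Week 52. It does not. It covers dose stability in patients already on MTX or sulfasalazine. The bar on other DMARDs comes from Table 5-1 and has no Week 52 limit.
- A reader might infer that 5.5.6 expressly keeps every patient given non-biologic rescue in the study. That is only an inference from biologics being the sole stated trigger for study discontinuation.
- A reader might infer that sites will treat the same patient differently. The wording makes this possible; nothing in the documents shows that it happened.
- The primary endpoint and all eight secondary efficacy objectives are at Week 16, the analysis is descriptive, and no test or decision in the visible text rests on the later rates.
- Rescue must be recorded (5.5.6), and all protocol deviations are tabulated (SAP 2.3.1). Only the link to response is missing.

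**Conclusion.** The contradiction is in the text and should be resolved. For a DMARD start or change made for worsening after Week 16, the protocol gives an unrestricted-rescue statement, a prohibition with no rescue exception, and an instruction to stop study treatment, with no order of precedence.

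The Week 16 primary and secondary efficacy results are unaffected. The descriptive Week 20 to 52 response rates could be affected, by 3.3 points per patient whose classification turns on staying or leaving. This takes n = 30 and the non-responder analysis.

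The total cannot be stated. One could be tempted to say that 12 of 30 patients (40%) are eligible for DMARD rescue under one section and none under the other, or that later rates shift by 10 to 20 points (3 or 6 patients). The documents support neither as an estimate. The 40% is the assumed ASAS 20 non-response rate, and missing ASAS 20 is not the same as needing a DMARD. The 3 and 6 have no source, and they also require that the patient stays in and then responds.

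**What to change.** **Protocol.** Reconcile 5.5.6, the methotrexate and sulfasalazine paragraphs of 5.5.7, 5.5.8 with Table 5-1, and 5.5.9. One rule should state whether a non-biologic DMARD start or dose change after Week 16 is allowed rescue or prohibited treatment, whether a new start of MTX or sulfasalazine counts as an unstable dose, and whether the patient continues study treatment and stays in the study. Which rule applies is for the sponsor to decide.

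**SAP.** With each Week 20 to 52 responder table, report the number of responders who had started or changed a DMARD by that visit. The existing non-responder and observed-case analyses can stay as they are.

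**Cost.** Protocol wording, plus one count from concomitant medication data that 5.5.6 and 5.5.7 already require sites to record. The SAP describes the Week 24 interim as done and the Week 52 analysis as still to come, so the count can still be added for Week 52, and it can be produced for the earlier visits from the same data.

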### **5.5.7 Concomitant treatment**

The investigator should instruct the patient to notify the study site about any new medications he/she takes after the patient was enrolled into the study. All medications, procedures and significant non-drug therapies (including physical therapy and blood transfusions) administered after the patient was enrolled into the study must be recorded.

Guidelines for the use of specific medications are provided below:

#### **Methotrexate**

Patients taking MTX ( $\leq 25$  mg/week) must be on a stable dose for at least 4 weeks before baseline and maintained stable until Week 52.

#### **Folic acid**

Patients on MTX must be taking folic acid supplementation before baseline and during the trial to minimize the likelihood of MTX associated toxicity.

### **Sulfasalazine**

Patients taking sulfasalazine ( $\leq 3$  g/day) must be on a stable dose for at least 4 weeks before baseline and maintained stable until Week 52.

### **Leflunomide wash-out with cholestyramine**

In case of leflunomide treatment, a drug wash-out of 8 weeks has to be performed. However, another wash-out procedure might be considered. Cholestyramine could be given orally to wash-out the drug at a dose of 8 g t.i.d. Cholestyramine reduced plasma levels of the active leflunomide metabolite by approximately 40% in 24 hours and by 49% to 65% in 48 hours in three healthy volunteers. The administration of cholestyramine is recommended in patients who require a drug elimination procedure. If a patient receives the dose of 8 g t.i.d. for 11 days, he/she could be safely randomized 4 weeks after the beginning of the 11 days treatment epoch.

### **Systemic corticosteroids**

Treatment with systemic corticosteroids is permitted if the dose was stable within the 2 weeks preceding baseline, up to a maximum daily dosage of 10 mg prednisone equivalent. Corticosteroid dose reductions below 10 mg prednisone equivalent are permitted after Week 16, although the corticosteroid dose should not be reduced rapidly.

Any change in the dose of systemic corticosteroids during the trial must be recorded on the corresponding eCRF page.

Intra-articular corticosteroids are not permitted within the 4 weeks preceding baseline and up to Week 16. After Week 16, no more than 1 joint per 24-week period may be injected. No single injection should exceed 40 mg of triamcinolone (or equivalent) and the total dose of intra-articular corticosteroid may not exceed 80 mg of triamcinolone (or equivalent) during any 52-week period. Injection of intra-articular steroids is not permitted within 8 weeks prior to Week 52.

### **Non-steroidal anti-inflammatory drugs (NSAIDs) (including COX-1 or COX-2 inhibitors) and acetaminophen/paracetamol**

Patients on regular use of NSAIDs or paracetamol/acetaminophen should be on stable dose for at least 2 weeks before baseline to allow inclusion in the study.

NSAIDs, low strength opioids or paracetamol/acetaminophen PRN can be taken during the study; however, patients should refrain from any intake during at least the 24 hours before a visit with disease activity assessment.

After the Week 16 assessments are completed, a change in the NSAID intake regimen is permitted.

Any change of the NSAID/paracetamol/acetaminophen treatment during the trial should be recorded on the corresponding eCRF page

### **5.5.8 Prohibited Treatment**

Use of the treatments displayed in [Table 5-1](#) is NOT allowed after the start of the washout period unless otherwise specified below.

Live vaccines should not be given until 12 weeks after last study treatment administration.

**Table 5-1      Prohibited treatment**

Prohibited treatments	Washout period (before BSL)
Etanercept*	4 weeks
Infliximab*	8 weeks
Adalimumab, golimumab, certolizumab*	10 weeks
Unstable dose of MTX or sulfasalazine (until Week 52)	4 weeks
Other DMARD (except MTX or sulfasalazine)	4 weeks
Leflunomide	8 weeks
Leflunomide with Cholestyramine washout	4 weeks
Unstable dose of NSAIDs (COX1 or COX2 inhibitors) (until Week 16)	2 weeks
Systemic corticosteroids > 10 mg prednisone equivalent** (until Week 16)	2 weeks
Intra-articular steroid injections (until Week 16)	4 weeks
Any investigational treatment or participation in any interventional trial	4 weeks or 5 half-lives (whichever is longer)
Analgesics other than paracetamol/acetaminophen or low strength opioids PRN	4 weeks
Live vaccinations	6 weeks

\* These agents fall under the category of biologic immunomodulators and are prohibited medications. Administration of these agents requires study discontinuation (see [Section 5.5.9](#)).

\*\* See details about corticosteroid management in [Section 5.5.7](#).

### **5.5.9      Discontinuation of study treatment**

Patients may voluntarily discontinue study treatment for any reason at any time.

They may be considered discontinued if they state an intention to withdraw, fail to return for visits, or become lost to follow-up for any other reason.

If premature discontinuation occurs for any reason, the investigator must make every effort to determine the primary reason for a patient's premature discontinuation from the study and record this information on the appropriate Study Phase Completion eCRF.

Patients who discontinue study should undergo an end of treatment visit (corresponds to the last visit for the patient's current period of treatment: e.g., Week 24, Week 52) at 4 weeks after last study treatment and then also return after an additional 8 weeks for a final follow-up visit, corresponding to Week F60 (12 weeks after last study treatment; see [Table 6-1](#)). The

final follow-up visit should be performed before any new treatment is initiated. For patients who are lost to follow-up (i.e., those patients whose status is unclear because they fail to appear for study visits without stating an intention to withdraw from the study), the investigator should show "due diligence" by documenting in the source documents steps taken to contact the patient, e.g., dates of telephone calls, registered letters, etc.

Patients who are prematurely discontinued from the study will not be replaced.

Study treatment must be discontinued under the following circumstances:

- Withdrawal of informed consent
- Emergence of the following adverse events:
  - a. Any severe or serious adverse event that is not compatible with administration of study medication, including adverse events that require treatment with prohibited co-medication
  - b. Onset of lymphoproliferative disease or any malignancy except for treated basal cell carcinoma, treated actinic keratoses, treated *in situ* carcinoma of the cervix or non-invasive malignant colon polyps which are being or have been removed
  - c. Life-threatening infection
  - d. Any laboratory abnormalities that in the judgment of the investigator are clinically significant and are deemed to place the patient at a safety risk for continuation in the study (A general guidance on clinically notable laboratory values is provided in [Appendix 1](#)).
  - e. Pregnancy
  - f. Use of any biologic immunomodulating agent except secukinumab
  - g. Any protocol deviation that results in a significant risk to the patient's safety

In addition to these requirements for study treatment discontinuation, the investigator should discontinue study treatment for a given patient if there is a lack of improvement or worsening of their symptoms, or if on balance, he/she thinks that continuation would be detrimental to the patient's well-being.

### **5.5.10 Withdrawal of consent**

Patients may voluntarily withdraw consent to participate in the study for any reason at any time.

Withdrawal of consent occurs only when a patient does not want to participate in the study anymore and does not want any further visits or assessments and does not want any further study related contacts and does not allow analysis of already obtained biologic material.

If a patient withdraws consent, the investigator must make every effort (e.g. telephone, e-mail, letter) to determine the primary reason for this decision and record this information. Study treatment must be discontinued and no further assessments conducted. All biological material that has not been analyzed at the time of withdrawal must not be used. Further attempts to contact the patient are not allowed unless safety findings require communicating or follow-up.

### **5.5.11 Loss to follow-up**

For patients whose status is unclear because they fail to appear for study visits without stating an intention to withdraw, the investigator should show "due diligence" by contacting the patient, family or family physician as agreed in the informed consent and by documenting in the source documents steps taken to contact the patient, e.g. dates of telephone calls, registered letters, etc. A patient should not be formally considered lost to follow-up until his/her scheduled end of study visit would have occurred.

